## Statistical Plan and Data Analysis

The randomized groups will be descriptively compared on baseline demographic and pain variables using descriptive statistics. In particular, groups will be considered well-balanced on a particular baseline variable if the standardized difference (difference in means or proportions divided by the pooled standard deviation) is less than  $\sqrt{2/n}$ , where  $n$  is the per-group sample size. The primary analysis will be modified intention-to-treat, in which all randomized subjects who received any of the study treatment will be included and retained in their respective treatment groups.

**Aim 1: Primary outcome.** We will assess the average causal effect of cryoneurolysis versus sham/placebo on phantom limb pain intensity (average pain over past 72 hours) at 4 months after the initial treatment using analysis of covariance to adjust for baseline pain intensity and any imbalanced baseline variables (see above). Results will be summarized as the least squares difference in means at 4 months and 95% confidence interval. Mean and standard deviation change from baseline intensity will also be summarized. Similar analyses will be conducted for the secondary outcomes of current/present, worst and least phantom pain, as well as average and worst residual limb pain.

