**Dropouts.** At most, about 7% of subjects in each group are expected to drop out of the study before reaching the 4-month primary outcome assessment (based on an unpublished pilot study of pre-emptive continuous peripheral nerve block use for surgical amputation, for which we observed 1 of 15). Since the current study will consist of volunteers traveling to the centers for enrollment and a treatment procedure, we expect even less. For those missing 4-month data we will use the last-observation-carried-forward method if the brief pain inventory was measured at 3 months. Otherwise, we will use intent-to-treat and conservatively assign the best observed score to the sham/control group and the worst score for the treated group subjects. We do not expect any appreciable effect of dropouts on either the power of the study or the unbiasedness of study results.

**Interim analyses.** We will conduct interim analyses to assess efficacy (rejecting null) and futility (rejecting alternative) at each 25% of the maximum enrollment using a group sequential procedure. Specifically, a gamma spending function will be used with parameters -4 and -2 for efficacy and futility, respectively. Thus, boundaries at the 1st through 4th analyses for efficacy (futility in parentheses) will be  $P \leq 0.0016$  ( $P > 0.9572$ ),  $P \leq 0.0048$  ( $P > 0.7186$ ),  $P \leq 0.0147$  ( $P > 0.2389$ ) and  $P \leq 0.0440$  ( $P > 0.0440$ ) (**Figures below**).

**Type I error.** We will use a parallel gatekeeping procedure to control the study-wide type I error at 0.05. For this procedure, we therefore *a priori* prioritize the study outcomes into ordered sets, as Aim 1, Aim 2a, Aim 2b and then Aim 2c. Analysis will proceed in that order, and testing will proceed through each “gate” to the next set if and only if at least one outcome in the current set reaches significance. The significance level for each set will be 0.05 times a cumulative penalty for non-significant results in previous sets (i.e., a “rejection gain factor” equal to the cumulative product of the proportion of significant tests across the preceding sets). Within a set, a multiple comparison procedure (Bonferroni correction) will be used as appropriate to control the type I error at the appropriate level. SAS statistical software (Carey, North Carolina), R programming language (The R Project for Statistical Computing) and East 5.3 software (Cytel Inc.) will be used for all analyses.

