**Sample size considerations.** Our sample size estimate is based on the primary specific aim of whether the addition of cryoneurolysis decreases phantom limb pain intensity resulting from an amputation compared with current standard-of-care treatment at 4 months following cryoneurolysis. Receiver operating characteristic curve analyses demonstrate that changes from baseline of at least 1.7 along a 10-point NRS accurately identified patients who rated improvements as “much improved” or more, compared with those who perceived no change or worsening following analgesic interventions. Multiple additional studies confirm this degree of reduction as clinically meaningful to individual patients with chronic pain. Meaningful group differences in the mean change would be somewhat smaller than important changes for individuals.

Therefore, we power our study to be able to detect group differences in mean change from baseline of 1.7 points or more on the NRS. Based on a conservative standard deviation estimate for each group of 3.0 at 4 months, a correlation of 0.50 between baseline and follow-up NRS, a two-sided test at the 0.05 significance level, power of 0.90, and 4 equally spaced analyses (3 interim and 1 final, as needed), a maximum of 72 subjects in each group (N=144 total) is required (East 5.3 software, Cytel Inc). The expected sample size for this group sequential design (i.e., average sample size over thousands of such trials, stopping when a boundary is crossed) is a total of 100 under the alternative and 102 under the null hypotheses. **Table 2** reports boundary crossing probabilities at each of the 4 analyses for this design, assuming that either the null or alternative hypotheses were true. For example, there is a cumulative 8%, 37% and 75% chance of crossing a boundary at the 1st, 2nd and 3rd analyses, respectively, if the alternative hypothesis were true. However, if the true standard

deviation at 4 months were smaller, say 2.5 instead of 3.0, then the cumulative probability of stopping for efficacy at the 1st, 2nd and 3rd analyses, respectively, would increase to 16%, 55% and 88% under the alternative hypothesis.

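### Filling subjects who miss both month 3 and month 4 with the best score in the sham arm and the worst in the treated arm biases the primary estimate against cryoneurolysis, at odds with the plan's statement that dropouts will not matter

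*Combined protocol and SAP*

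**What the plan says.** All references are to section 9 of the combined protocol and SAP, from Statistical Plan and Data Analysis onward.

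- **Target.** Aim 1 states: "We will assess the average causal effect of cryoneurolysis versus sham/placebo on phantom limb pain intensity" at 4 months, by analysis of covariance (ANCOVA) on baseline pain. The analysis set is modified intention-to-treat and keeps every randomized subject who received any treatment. The Crossover phase paragraph adds that the first phase is where the unbiased effect will come from.
- **Missing month 4.** Dropouts prescribes the "last-observation-carried-forward method if the brief pain inventory was measured at 3 months". Failing that, the plan will "conservatively assign the best observed score to the sham/control group and the worst score for the treated group subjects". Neither step is labelled a sensitivity analysis, and no other method is given.
- **Expectation.** The same paragraph ends: "We do not expect any appreciable effect of dropouts on either the power of the study or the unbiasedness of study results". It puts dropout before month 4 at no more than about 7% per group, from a pilot study "for which we observed 1 of 15".
- **Interim looks.** "We will conduct interim analyses to assess efficacy (rejecting null) and futility (rejecting alternative) at each 25% of the maximum enrollment". The paragraph does not say how missing month-4 scores are treated at those looks.
- **Sizing.** Sample size considerations says "power our study to be able to detect group differences in mean change from baseline of 1.7 points or more on the NRS", with a maximum of 72 per group. The inputs begin: "Based on a conservative standard deviation estimate for each group of 3.0 at 4 months, a correlation of 0.50 between baseline and follow-up NRS".

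**The concern.** The pain scale runs from 0 to 10 and higher is worse. A sham subject missing both visits is given a low score and a treated subject a high one, so the direction of the fill depends on the arm. On average it pushes the estimated benefit down, whatever caused the dropout.

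Three things are at stake: the reported difference and confidence interval, the chance of detecting a true effect, and the stopping decisions. The rule lowers false efficacy claims. It is not conservative in the other direction: the test is two-sided, and with no true effect the rule raises the chance of declaring sham better.

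Two things that set the size are left open. One is whether the best observed score is taken over the sample, the arm or the subject's own record. The other is whether the fill is applied at the three interim looks.

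**Working it through.** **1. Reproduce the plan's design.** Inputs from Sample size considerations, Interim analyses and Table 2: SD 3.0, correlation 0.50, difference 1.7, two-sided 0.05, four equally spaced looks, efficacy limits P ≤ 0.0016/0.0048/0.0147/0.0440, interim futility limits P > 0.9572/0.7186/0.2389.

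- SD of change = √(2 × 9 × (1 − 0.5)) = 3.0. Integrating over the four looks gives 71.7 per arm for 90% power (plan: 72). Expected total N is 100.6 under the alternative and 102.6 under the null (plan: 100 and 102).
- The plan was therefore sized on a change-score basis. ANCOVA has residual SD 3.0 × √(1 − 0.5²) = 2.60, and power at 72 per arm is then about 96%.

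**2. Shift in the estimate.** Let k of 72 subjects per arm miss both visits, with fill values *best* and *worst*. The treated mean rises by (k/72)(worst − treated mean) and the sham mean falls by (k/72)(sham mean − best). The sham-minus-treated difference δ therefore falls by

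(k/72) × [(worst − best) + δ],

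whatever the arm means. With extremes 0 and 10 and δ = 1.7 this is 11.7/72 = 0.1625 per pair. With extremes 2 and 8 it is 7.7/72 = 0.107.

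**3. How many subjects.** The documents give no count. The full 7% is 0.07 × 72 = 5.04 per arm, but it covers every dropout before month 4, including those with a month-3 score. Five per arm is thus the upper scenario under the plan's own rate, and zero is possible. The rate itself rests on 1 of 15 (exact 95% interval 0.2% to 32%).

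**4. Power.** Simulation with the inputs of step 1, extremes 0 and 10, a normal scale, and affected subjects placed at random in accrual order. The baseline and sham means of 5 are assumed; a baseline mean of 6.5 changes power by 1 point or less. Repeat runs agree within about 2 points.

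| Affected per arm | 0 | 1 | 3 | 5 |
|---|---|---|---|---|
| Expected difference | 1.70 | 1.54 | 1.21 | 0.89 |
| ANCOVA, 95% CI coverage of 1.7 at full sample | 95% | 94% | 85% | 64% |
| ANCOVA power, rule at every look | 96% | 91-92% | 70% | 37-38% |
| ANCOVA power, rule at final look only, completers at interims | 96% | 93% | 84% | 78% |
| Change-score power, rule at every look | 90% | 82% | 58% | 30% |
| Change-score power, rule at final look only | 90% | 84% | 72% | 65% |

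**5. Why the two interim rules differ.** At five per arm under ANCOVA, efficacy is declared before the final look in about 78% of trials with completers at interims, but in about 16% with the fill. With futility stopping switched off, power with the rule at every look is 41% instead of 37%. Lost early efficacy crossings are therefore the main cause; futility stops add only about 1-4 points.

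**6. No true effect.** The shift is 10/72 = 0.14 points per pair toward sham. At five per arm, rejection in favour of sham is about 20-29% (every look) or 10% (final look only), against about 2%. At one per arm it is about 3-4%.

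**7. Own-score reading.** If best and worst mean the subject's own earlier scores, five per arm costs about 0.3-0.4 points, in the same direction. ANCOVA power is then about 79-84% (every look) or 84-88% (final look only).

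**The case against.** The plan calls the fill conservative and so discloses its direction, and against a false efficacy claim it is. Its closing sentence is a forecast resting on few dropouts; the plan expects fewer than 7%, follow-up is by telephone, and those with a month-3 score never meet the fill. With one affected subject per arm, the planned ANCOVA still has 91-93% power, above the 90% target, and 94% coverage. All of this stands, and it limits the severity. It does not reconcile the rule with the promise of an unbiased effect: the forecast holds only if almost nobody meets the rule.

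A reader might infer more than the documents support:

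- **That the trial will lose most of its power.** The 37-38% needs the full 7% to drop out, none with month 3, sample-wide extremes of 0 and 10, and the fill at every look. None of these is stated.
- **That a single pair takes power below 90%.** This is so on the change-score sizing basis (82-84%). The planned primary analysis is ANCOVA; change scores are only a fallback.
- **That futility stopping drives the loss.** Step 5 shows otherwise.
- **That carrying month 3 forward is also at fault.** Nothing computed here bears on that.
- **That every affected subject moves the estimate.** This holds on average; a sham subject whose unseen score equals the best observed moves nothing.

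**Conclusion.** The concern holds in a conditional form. For subjects missing both months 3 and 4, the primary analysis contains a fill that on average works against cryoneurolysis. It conflicts with the stated aim of an unbiased effect, and with the expectation about dropouts once more than a very few subjects are affected.

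With extremes 0 and 10 the cost is 0.16 points per affected pair. The consequence for power under ANCOVA runs from small at one per arm, through 70-84% at three, to 37-78% at five, depending on interim handling. The result rests on an assumed number missing both visits, on how the best observed score is read, and on what is done at the interim looks; the documents settle none of these. If every dropout has a month-3 score the bias is nil. This should be fixed, but it does not undermine a positive efficacy finding.

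**What to change.** - For subjects missing both visits, replace the best/worst fill in the primary analysis with a method valid under missing at random on data already collected. Either use multiple imputation from baseline and the earlier visits, feeding the planned ANCOVA, or a baseline-adjusted repeated-measures model with the month-4 contrast. State that it also applies at the interim looks.
- Keep the best/worst fill as a labelled sensitivity analysis, with the best observed score defined, and add a tipping-point analysis.
- Replacing the month-3 carry-forward as well is optional; the figures here do not argue for it.
- Rest the sentence on power and unbiasedness on the new method. If it gives a power with 7% missing, it should name the basis: about 87-88% on the change-score sizing basis, about 95% under the planned ANCOVA.

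The cost is SAP wording and some programming, with no new visits or data. The primary analysis would then assume missing at random, which the retained sensitivity analyses would test.

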**Table 2. P-value boundaries and boundary crossing probabilities for group sequential design**

Fraction of Maximum Accrual	Cumulative Accrual	Alpha Spent	Beta Spent	P-value Boundaries		Boundary Crossing Probabilities	
				H0	H1	Under H0	Under H1
0.250	36	0.002	0.010	0.0016	0.9572	0.044	0.083
0.500	72	0.006	0.027	0.0048	0.7186	0.269	0.290
0.750	108	0.018	0.054	0.0147	0.2389	0.485	0.379
1.000	144	0.050	0.100	0.0440	0.0440	0.202	0.248

## 10. HUMAN SUBJECTS

Approximately 60 subjects will be enrolled at UC San Diego, of approximately 200 participants at all sites.

**Inclusion criteria:** Adult patients of at least 18 years of age, (1) with a lower limb traumatic or surgical amputation at least 12 weeks prior to enrollment distal to the hip (femoral head remaining); (2) who experience at least moderate phantom limb pain—defined as a 3 or higher on the Numeric Rating Scale (NRS; 0-10, 0= no pain; 10=worst imaginable pain)—at least daily for the previous 2 months. (3) accepting of a cryoneurolysis procedure; and, (4) willing to avoid both changes to their analgesic regimen as well as elective surgical procedures from 1 month prior to and at least 4 months following the initial cryoneurolysis procedure.

**Exclusion criteria:** (1) allergy to amide local anesthetics; (2) pregnancy; (3) incarceration; (4) inability to communicate with the investigators; (5) morbid obesity (body mass index > 40 kg/m^2); and, (6) possessing any contraindication specific to cryoneurolysis such as a localized infection at the treatment site, cryoglobulinemia, cold urticaria and Reynaud's Syndrome.

## 11. RECRUITMENT AND PROCEDURES PREPARATORY TO RESEARCH

Study subjects will be identified by each of the enrolling centers from four sources:

**1. Databases.** Databases will be examined by non-investigator database managers following Institutional Review Board approval, and subsequently queried quarterly. The site directors will provide database managers with Institutional Review Board-approved letters describing the study with investigator contact information sealed in envelopes with postage applied. Database managers will then use existing databases to identify individuals with a prior amputation and apply address labels to the supplied letters and mail them—this is to adhere to current HIPAA rules. Individuals who are interested in the study will be directed to contact the study investigators or research coordinators for a thorough description of the study purpose and protocol. Of note, all U.S. service members with a limb amputation during Operation Iraqi Freedom and Operation Enduring Freedom are included in an amputee-specific database, regardless of inclusion in surgical or chronic pain databases; but, the information within this database is not available for clinical investigations to protect patient privacy. We will strive to reach all of these individuals using the additional methods described below to ensure

that all U.S. military personnel are informed of the study and have the opportunity to participate.

**2. Clinics.** Each site director will identify and meet quarterly with clinic (amputee-specific, surgical, and chronic pain) personnel to both inservice them on the study protocol as well as provide Institutional Review Board-approved written information describing the investigation that may be given to prospective subjects during clinic visits. Clinic patients will come into contact with their healthcare providers during regularly-scheduled clinic visits, and these providers will briefly describe the study and offer written information to patients with phantom limb pain who voice interest in the study. Patients who are interested in the study will be required to give permission for a research coordinator to contact them to adhere to Health Insurance Portability and Accountability Act (HIPAA) requirements.

**3. Advertisements.** The Primary Investigator will place Institutional Review Board-approved study advertisements within print and web-based publications that are frequently read by the target population. Additionally, site directors will provide similar Institutional Review Board-approved advertising material to the leaders of local and regional amputee focus/support groups. Individuals who are interested in the study will be directed to contact the study investigators or research coordinators for a thorough description of the study purpose and protocol. In addition, Institutional Review Board-approved advertisements will be placed and a study-specific information page created within Facebook, which has over 1-billion members. Of note, the United States Army, Navy, Air Force, and Marines all have dedicated Facebook information pages. Information on how to volunteer for the study will also be placed in relevant Twitter feeds, such as the Clinical Trial Spotlight San Diego, and Clinical Connection, free portals for finding clinical trials. Twitter users (over 300-million registered users) looking for trials will be able to access contact information to the study, and link to the Facebook page for additional information.

**4. ClinicalTrials.gov.** The trial will be prospectively registered on the ClinicalTrials.gov website. One of the main purposes of trial registries is to provide the general population access to available ongoing investigations. Contact information for the site directors will be included on the website so that prospective subjects may receive a thorough description of the study purpose and protocol. Which site director subjects contact is up to the subjects themselves, because all will be listed on the website. However, for individuals desiring enrollment, site directors will suggest the optimal treatment center based on geographic location and military status (e.g., civilians can be treated exclusively at one of the civilian enrolling centers).

Once a prospective subject contacts a site director or research coordinator by telephone or email, they will be provided information on the study purpose and protocol, as well as have any questions answered. Inclusion/exclusion criteria will be reviewed and documented on a form to identify subject eligibility according to these criteria. If a prospective subject is excluded for any reason, the reason for exclusion will be recorded, but no patient identifying information will be recorded. Candidates who meet inclusion and exclusion criteria and desire study enrollment will be scheduled for their initial study treatment. Written informed consent will be attained prior to any measurements or procedures the morning of the initial treatment (see below for a detailed description of the informed consent process).

**Recruitment of Active Duty Military Personnel.** The Chain of Command will not be involved in the recruitment of military personnel; and will in no way be asked to encourage or order soldiers to participate in the trial. As per Department of Defense Directive 3216.2, an ombudsman will be present if any group briefings of Active duty personnel are scheduled, to help ensure that those

present understand that study participation is completely voluntary and will not influence their careers or standing within the military.

**Study Compensation.** To help compensate study subjects for their time and defray travel expenses, participants will receive \$500 following each study treatment prior to discharge (initial and the optional crossover). We believe that this compensation amount is both fair and does not provide undue inducement. The University of California San Diego Institutional Review Board approved similar amounts for subjects in clinical trials of similar time, risk and duration. Currently, 24 USC 30 limits payments to Active Duty military personnel for participation in research while on duty to blood donations (which are not required for the proposed investigation). However, military personnel who are on official military leave status *may* receive compensation for study participation, and will do so at the same level and on the same schedule as described for civilians and Veterans.

**Recruitment and advertisement materials.** These materials are being developed and will be provided to the IRB prior to use. Each of the 7 enrolling centers will include information specific to that center. We believe that these documents accurately reflect the study and are not coercive or offer undue inducements.

## 12. INFORMED CONSENT

Once a prospective subject contacts a site director or research coordinator by telephone or email, they will be provided information on the study purpose and protocol, as well as have any questions answered. Candidates who meet inclusion and exclusion criteria and desire study enrollment will be scheduled for their initial treatment. Written informed consent will be attained prior to any measurements or procedures the morning of the initial treatment. Each site director is responsible for ensuring that written, informed consent is obtained from every subject at his respective enrolling center. Clinical research coordinators—also one for each enrolling site—will be specifically trained by the site directors to provide informed consent followed by documentation of informed consent using an Institutional Review Board-approved informed consent form. When subjects present for their initial treatment, research coordinators will provide and attain written informed consent. This will occur in private patient care rooms, so that subjects may feel comfortable asking questions of the research coordinator. If a subject desires—or if there is a question that a research coordinator cannot answer—the site director will be called in by the research coordinator to discuss the study directly with the subject.

We do not foresee any issues relevant to the mental capacity of the potential human subjects. Written, informed consent will be attained prior to any study procedures or measurements. Following a history and physical by the site director, subjects will have an intravenous line inserted, external monitors placed, oxygen delivered by face mask, and conscious sedation provided with minimal intravenous fentanyl (opioid) and midazolam (benzodiazepine), when applicable (not all subjects require sedation). This sedation is to increase the comfort of subjects during probe insertion. Therefore, subjects will not be sedated until following the written, informed consent process is completed.

Subjects will be provided privacy and time for decision making both in the study description/explanation telephone call to the site director or research coordinator, as described above; and also the morning of the initial treatment using a private patient care room to again review the study, informed consent form, and answer any remaining subject questions. As noted previously,

subjects may speak with the site director by telephone from initial contact through the morning of treatment; and, will have access during and following the treatment(s) with cellular phone and pager numbers provided upon discharge.

This study protocol has follow-up data-collection telephone calls a maximum of 1 year following the initial study treatment, so repeated informed consent following the initial consent is unnecessary, as opposed to multi-year, longer-term clinical trials.

Surrogate consent will not be accepted; therefore, if human subjects cannot provide consent on their own, they will not be offered study enrollment. Consent by an individual's Legally Authorized Representative is unacceptable for study enrollment. Of note, minors (age < 18 years) will not be offered enrollment, as explained in Section 6b (Inclusion/Exclusion Criteria). Therefore, assent will not be accepted during the informed consent process.

